**9.8 Visit 6 (Day 21)**

1. Review and record changes to concomitant medications.
2. Perform and record vital signs.
3. Perform and record oximetry.
4. Perform and record urine pregnancy test
5. Perform and record fractional exhaled nitric oxide (FeNO) measurement.
6. Perform and record spirometry.
7. Perform and record post-bronchodilator reversibility.
8. Perform and record plethysmography with bronchodilation.
9. Obtain a CT scan of the thorax
10. Collect induced sputum sample
11. Collect blood for clinical laboratory tests.
12. Schedule Visit 7 after 8 weeks.

**9.9 Visit 7 (Day 77)**

1. Review and record changes to concomitant medications.
2. Perform and record vital signs.
3. Perform and record oximetry.
4. Perform and record urine pregnancy test.
5. Perform and record fractional exhaled nitric oxide (FeNO) measurement.
6. Perform and record spirometry.
7. Perform and record post-bronchodilator spirometry.
8. Obtain a CT scan of the thorax.
9. Collect induced sputum sample.
10. Collect blood for clinical laboratory tests.
11. Schedule Visit 8 within 1 week.

**9.10 Visit 8 (Day 84)**

1. Review and record changes to concomitant medications.
2. Perform and record vital signs.
3. Perform and record oximetry.
4. Perform and record urine pregnancy test
5. Perform and record fractional exhaled nitric oxide (FeNO) measurement.
6. Perform and record spirometry.
7. Perform and record post-bronchodilator reversibility.
8. Perform and record plethysmography with bronchodilation.
9. Provide education on use of personal nebulizer and administration of study medication.
10. Administer first two treatments of study drug treatment, spaced 4-6 hours. FEV1 measurements should be taken before and after each treatment.
11. Dispense study drug and initiate study diary if subject's post-treatment FEV1 is greater than 80% of pre-treatment FEV1
12. Schedule participant for phone follow-up in 3-5 days and visit 5 in 7 days.

**9.11 Phone follow-up (Day 86, 87, or 88)**

1. Administer questionnaire to monitor for treatment related side effects.

**9.12 Visit 9 (Day 91)**

1. Record any adverse experiences and/or review participant diary for adverse experiences.
2. Perform abbreviated physical examination.
3. Review and record changes to concomitant medications.
4. Record vital signs.
5. Perform and record oximetry.
6. Perform and record urine pregnancy test
7. Perform and record spirometry.
8. Perform and record post-bronchodilator spirometry.
9. Review diary card.
10. Dispense remaining 7 days of study drug.
11. Schedule participant for Visit 10 in 7 days.

**9.13 Visit 10 (Day 98)**

1. Review and record changes to concomitant medications.
2. Perform and record vital signs.
3. Perform and record oximetry.
4. Perform and record urine pregnancy test
5. Perform and record fractional exhaled nitric oxide (FeNO) measurement.
6. Perform and record spirometry.
7. Perform and record post-bronchodilator reversibility.
8. Perform and record plethysmography with bronchodilation.
9. Obtain a CT scan of the thorax
10. Collect induced sputum sample
11. Collect blood for clinical laboratory tests.

**9.14 Early Withdrawal Visit**

1. Record any Adverse Experiences and/or Review participant diary for adverse experiences and exclusionary medication use.
2. Review and record changes to concomitant medications.
3. Perform abbreviated physical examination.
4. Perform and record vital signs.
5. Perform and record oximetry.
6. Perform and record urine pregnancy test.
7. Perform and record spirometry.
8. Perform and record post-bronchodilator spirometry.
9. Collect any unused study drug.
10. Review dairy card.
11. Perform and record plethysmography with bronchodilation\*
12. Obtain a CT scan of the thorax\*
13. Collect induced sputum sample\*

#### 14. Collect blood for clinical laboratory tests\*

\*Subjects will only be eligible to complete post-treatment plethysmography, CT scan, sputum induction and blood collection if they completed a minimum of five treatment days or 10 treatments.

## 10 ADVERSE EXPERIENCE REPORTING AND DOCUMENTATION

### 10.1 Adverse Events

An adverse event (AE) is any untoward medical occurrence in a clinical investigation of a patient administered a pharmaceutical product and that does not necessarily have a causal relationship with the treatment. An AE is therefore any unfavorable and unintended sign (including an abnormal laboratory finding), symptom or disease temporally associated with the administration of an investigational product, whether or not related to that investigational product. An unexpected AE is one of a type not identified in nature, severity, or frequency in the current Investigator's Brochure or of greater severity or frequency than expected based on the information in the Investigator's Brochure.

The Investigator will probe, via discussion with the participant, for the occurrence of AEs during each participant visit and record the information in the site's source documents. Adverse events will be recorded in the participant CRF. Adverse events will be described by duration (start and stop dates and times), severity, outcome, treatment and relation to study drug, or if unrelated, the cause.

#### AE Severity

The National Cancer Institute's Common Terminology Criteria for Adverse Events (CTCAE) Version 3.0 should be used to assess and grade AE severity, including laboratory abnormalities judged to be clinically significant. The modified criteria can be found in the study manual. If the experience is not covered in the modified criteria, the guidelines shown in Table below should be used to grade severity. It should be pointed out that the term "severe" is a measure of intensity and that a severe AE is not necessarily serious.

**Table 3. AE Severity Grading**

Severity (Toxicity Grade)	Description
Mild (1)	Transient or mild discomfort; no limitation in activity; no medical intervention or therapy required. The participant may be aware of the sign or symptom but tolerates it reasonably well.
Moderate (2)	Mild to moderate limitation in activity, no or minimal medical intervention/therapy required.
Severe (3)	Marked limitation in activity, medical intervention/therapy required, hospitalizations possible.
Life-threatening (4)	The participant is at risk of death due to the adverse experience as it occurred. This does not refer to an experience that hypothetically might have caused death if it were more severe.

#### AE Relationship to Study Drug

The relationship of an AE to the study drug should be assessed using the following the guidelines in Table .

**Table 4. AE Relationship to Study Drug**

Relationship to Drug	Comment
Definitely	Previously known toxicity of agent; or an event that follows a reasonable temporal sequence from administration of the drug; that follows a known or expected response pattern to the suspected drug; that is confirmed by stopping or reducing the dosage of the drug; and that is not explained by any other reasonable hypothesis.
Probably	An event that follows a reasonable temporal sequence from administration of the drug; that follows a known or expected response pattern to the suspected drug; that is confirmed by stopping or reducing the dosage of the drug; and that is unlikely to be explained by the known characteristics of the participant's clinical state or by other interventions.
Possibly	An event that follows a reasonable temporal sequence from administration of the drug; that follows a known or expected response pattern to that suspected drug; but that could readily have been produced by a number of other factors.
Unrelated	An event that can be determined with certainty to have no relationship to the study drug.

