### 2.1 Risk / Benefit Assessment

**Risk:** Inhaled n-acetylcysteine (NAC) is approved for the treatment of mucus associated airway disease, including asthma. The main side effect from inhaled n-acetylcysteine (NAC) is bronchospasm. We find that co-administering NAC and albuterol effectively prevents excessive bronchoconstriction in asthmatic patients. Specifically, in eight asthmatics that were given doses of 20% NAC as high as 3 mL together with 3 mL of albuterol, the largest FEV1 decline was 6%.

**Benefit:** Mucus plugs cause airway obstruction and symptoms of dyspnea. The role of mucolytics in decreasing plugs and increasing FEV1 has not been well studied. Our preliminary data, utilizing CT imaging and a novel scoring system, can identify and target a

subgroup of patients who may benefit from inhaled mucolytic treatment more so than the asthmatic population as a whole.

To minimize risk, study participants will be administered the first two treatments under the supervision of the study team in the Airway Clinical Research Center and will only be eligible to remain in the study if their post-treatment FEV1s are greater than 80% of their pre-treatment, pre-bronchodilator FEV1.

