### **8.1.9 Spirometry**

Spirometry will be performed at visits 1-10 in accordance with the current American Thoracic Society recommendations for the performance and interpretation of tests.

Associated risks include the following:

- Likely (>10%)
  - Shortness of breath or cough during the six-second exhalation part.

- Less Likely (<5%)
  - Wheezing and chest tightness.
- Rare but serious (<1%)
  - Syncope

In an effort to minimize risk to participants will be seated during the procedure to reduce any injury should a participant become dizzy and fall. Coordinators will have albuterol available to administer to participants who develop wheeze or shortness of breath following spirometry.

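### Table 4 rates any known toxicity *Definitely* drug-related and leaves a reaction new in nature without a related grade, so the relation-to-drug rating does not discriminate for bronchospasm

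*Combined protocol and SAP*

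**What the plan says.** Sections 8.1.17 and 10.1 require the relation to study drug to be recorded for each adverse event, and the text above Table 4 says its guidelines should be used. The table has four grades.

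- *Definitely* begins "Previously known toxicity of agent; or an event that follows a reasonable temporal sequence from administration of the drug". It then adds a recognised response pattern, confirmation by stopping or reducing the drug, "and that is not explained by any other reasonable hypothesis".
- *Probably* asks for timing, pattern and confirmation by stopping or reducing, in an event "that is unlikely to be explained by the known characteristics of the participant's clinical state or by other interventions".
- *Possibly* asks for timing, in an event "that follows a known or expected response pattern to that suspected drug; but that could readily have been produced by a number of other factors".
- The last grade, *Unrelated*, is "An event that can be determined with certainty to have no relationship to the study drug".

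There is no grade for unlikely or not assessable. Section 2.1 states: "The main side effect from inhaled n-acetylcysteine (NAC) is bronchospasm". Section 10.1 foresees new kinds of event: "An unexpected AE is one of a type not identified in nature, severity, or frequency in the current Investigator's Brochure".

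**The concern.** The table fails in two places.

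The first is the top grade. If event type alone is enough for *Definitely*, the assessor has no reason to weigh anything else. That would matter little for a toxicity rarely seen without the drug. Bronchospasm, however, is also a feature of the disease under study. The protocol lists rival causes itself: section 8.1.9 gives "Wheezing and chest tightness" as a risk of spirometry, section 8.1.12 lists wheeze and, rarely, a severe asthma attack after sputum induction, and section 8.1.2 says medication holds can worsen asthma control. A bronchospasm on saline, in the washout or straight after sputum induction would carry the same top rating as one caused by NAC.

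The second is the absence of a place for a reaction not seen before. Such an event is among those for which a case-level judgement is most wanted, and the scale offers no related grade for it.

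What is at stake is the meaning of a field that sites must complete for every adverse event: saturated for the main expected harm, and unavailable for a new one.

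**Working it through.** The plan gives no figure on this point, so the check is of the wording. Table 4, condition by condition:

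| Grade | Known toxicity alone enough | Timing | Recognised pattern | Improves on stopping or reducing | Other causes |
|---|---|---|---|---|---|
| *Definitely*, first limb | yes | not asked | not asked | not asked | not asked |
| *Definitely*, second limb | no | required | required | required | none reasonable |
| *Probably* | no | required | required | required | unlikely |
| *Possibly* | no | required | required | not asked | readily available |
| *Unrelated* | no | certainty of no relationship | | | |

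**Why the first limb stands alone.** The 'or' introduces a new noun, 'an event', and the conditions that follow describe that noun. They do not reach back to the clause before the 'or'.

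**Enumeration.** Describe an event by known toxicity (yes/no), timing (yes/no), recognised pattern (yes/no), improvement on stopping (yes/no) and other explanation (none, unlikely, readily available). Assume that a known toxicity follows a recognised pattern and that unrelatedness is not certain. Each group below then has 2 × 2 × 3 = 12 profiles.

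- Known toxicity: 12 of 12 meet *Definitely*. Of these, 2 also meet *Probably* and 2 also meet *Possibly*, so the grades are not mutually exclusive.
- New in nature (not a known toxicity, no recognised pattern): 0 of 12 meet any related grade, even with good timing, improvement on stopping and no other explanation.
- Not a known toxicity but with a recognised pattern: 4 of 12 get a related grade. Of the 8 left over, 6 lack timing. The other 2 are well timed, but did not improve on stopping and have no ready alternative cause.

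**Other reading of the 'or'.** If the later conditions bind both limbs, only 2 of the 12 known-toxicity profiles meet *Definitely*, one of them without plausible timing. The new-type count stays at 0 of 12.

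**Illustration only.** Suppose a background rate q of bronchospasm-type events per 14-day period, with 36 patients independent of each other and NAC without effect. The chance of at least one *Definitely* rating during the saline periods is 1 − (1 − q)^36:

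- q = 2%: 1 − 0.98^36 = 0.517
- q = 5%: 1 − 0.95^36 = 0.842
- q = 10%: 1 − 0.90^36 = 0.977

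These rates are assumptions. Sections 8.1.9 and 8.1.12 put wheeze below 5% for each procedure, but the documents give no background rate per treatment period. The illustration also counts each background event as bronchospasm.

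**The case against.** The best defence is that Table 4 is offered as guidelines, and a sensible investigator would apply the later conditions to both limbs. That reading removes most of the first defect. It leaves the second untouched, and wording that two sites can read in two ways still needs repair.

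A stronger objection is that little depends on the rating, and this largely stands.

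- The synopsis sets the safety evaluation as the incidence of adverse events of any cause. No analysis restricted to related events is specified, so a reader might infer that planned drug-related results would be wrong, but the plan promises none.
- A reader might infer that this field is the trial's only attribution of harm. The documents do not support that: the trial is a double-blind placebo crossover, FEV1 is taken before and after each supervised dose in both periods (Visits 4 and 8), and a cause is recorded for events judged unrelated.
- A reader might infer that reporting of unexpected reactions would fail. Section 10.2.1 documents serious events irrespective of relatedness, section 15.2 reports them regardless of causality, and neither section 5.3 nor item 8 of section 15.5 refers to Table 4.
- A reader might infer that no unexpected event can be rated as related. Section 10.1 also counts events unexpected in severity or frequency. A known toxicity of unusual severity does have a related grade; the gap is for events new in nature.

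**Conclusion.** The concern holds, with limited reach. On its natural reading Table 4 rates every known toxicity *Definitely* related, so the case-level rating does not discriminate for bronchospasm-type events. It would go too far to say that it fails for all events. An event new in nature has no related grade on either reading of the 'or', and is *Unrelated* only with certainty.

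The effect is confined to the relation-to-drug field. The comparison of all adverse events, the reporting of serious events and the primary endpoint are unaffected. The conclusion rests on the wording and on section 2.1 naming bronchospasm; the percentages are illustrations and carry no weight in it. The text between sections 10.2.1 and 11, where the contents list places Medical Monitoring, was not available to me, so any rule there that uses relatedness is unchecked.

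**What to change.** Make three edits to Table 4.

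1. *Definitely*: delete the opening known-toxicity clause and its 'or', so that all four remaining conditions are needed.
2. *Possibly*: define it as an event with plausible timing for which a drug cause cannot be excluded and which does not meet *Probably* or *Definitely*. Both existing conditions must go: the recognised pattern, and the ready availability of other causes. Removing the pattern alone would still exclude a new, well-timed reaction with no rival explanation. Removing both also gives a related grade to well-timed events without improvement on stopping, including a post-dose bronchospasm when the drug was not stopped.
3. *Unrelated*: define it as an event without plausible timing, or one clearly explained by another cause such as a study procedure or a medication hold.

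Check on the same profiles, where no event is clearly explained by another cause and the highest grade met is assigned. Known toxicity: 1 *Definitely*, 1 *Probably*, 4 *Possibly* and 6 *Unrelated* (no plausible timing), total 12. New in nature: 6 *Possibly* and 6 *Unrelated*, total 12. No profile in either group is left without a grade.

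The cost is one table, the matching CRF help text and fewer *Definitely* ratings. Events already rated must be re-rated while the blind holds, or ratings before and after the change will not be comparable.

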## 10.2 Serious Adverse Experiences (SAE)

An SAE is defined as any AE occurring at any dose that results in any of the following outcomes:

- death
- a life-threatening adverse experience
- inpatient hospitalization or prolongation of existing hospitalization
- a persistent or significant disability/incapacity
- a congenital anomaly/birth defect

Other important medical events may also be considered an SAE when, based on appropriate medical judgment, they jeopardize the participant or require intervention to prevent one of the outcomes listed.

### 10.2.1 Serious Adverse Experience Reporting

The study site will document all SAEs that occur (whether or not related to study drug) per [UCSF CHR Guidelines](#). The collection period for all SAEs will begin after informed consent is obtained and end after procedures for the final study visit have been completed.

In accordance with the standard operating procedures and policies of the local Institutional Review Board (IRB)/Independent Ethics Committee (IEC), the site investigator will report SAEs to the IRB/IEC.

## **11 DISCONTINUATION AND REPLACEMENT OF PARTICIPANTS**

### **11.1 Early Discontinuation of Study Drug**

A participant may be discontinued from study treatment at any time if the participant, the investigator, or the Sponsor feels that it is not in the participant's best interest to continue. The following is a list of possible reasons for study treatment discontinuation:

Participant withdrawal of consent

Participant is not compliant with study procedures

Adverse event that in the opinion of the investigator would be in the best interest of the participant to discontinue study treatment

Protocol violation requiring discontinuation of study treatment

Lost to follow-up

Sponsor request for early termination of study

Positive pregnancy test (females)

If a participant is withdrawn from treatment due to an adverse event, the participant will be followed and treated by the Investigator until the abnormal parameter or symptom has resolved or stabilized.

All participants who discontinue study treatment should come in for an early discontinuation visit as soon as possible.

All participants are free to withdraw from participation at any time, for any reason, specified or unspecified, and without prejudice.

Reasonable attempts will be made by the investigator to provide a reason for participant withdrawals. The reason for the participant's withdrawal from the study will be specified in the participant's source documents. Refer to Section 10 for early termination procedures.

If the participant completes five treatment days or 10 treatments they will be eligible to complete post-treatment plethysmography, CT scan, sputum induction and blood collection during a post-treatment termination visit. If they complete less than five treatment days or 10 treatments. Refer to Section 10 for early termination procedures.

### **11.2 Withdrawal of Participants from the Study**

A participant may be withdrawn from the study at any time if the participant, the investigator, or the Sponsor feels that it is not in the participant's best interest to continue.

All participants are free to withdraw from participation at any time, for any reason, specified or unspecified, and without prejudice.

Reasonable attempts will be made by the investigator to provide a reason for participant withdrawals. The reason for the participant's withdrawal from the study will be specified in the participant's source documents. As noted above, participants who discontinue study

treatment early (i.e., they withdraw prior to Visit 10) should have an early discontinuation visit. Refer to Section 10 for early termination procedures.

### **11.3 Replacement of Participants**

Participants who withdraw from the study treatment will be replaced.

Participants who withdraw from the study will be replaced.

## **12 PROTOCOL VIOLATIONS**

A protocol violation occurs when the subject or investigator fails to adhere to significant protocol requirements affecting the inclusion, exclusion, subject safety and primary endpoint criteria. Protocol violations for this study include, but are not limited to, the following:

- Failure to meet inclusion/exclusion criteria

- Use of a prohibited concomitant medication

Failure to comply with Good Clinical Practice (GCP) guidelines will also result in a protocol violation. The Sponsor will determine if a protocol violation will result in withdrawal of a subject.

When a protocol violation occurs, it will be discussed with the investigator and a Protocol Violation Form detailing the violation will be generated. This form will be signed by a Sponsor representative and the Investigator. A copy of the form will be filed in the site's regulatory binder and in the Sponsor's files.

## **13 DATA SAFETY MONITORING**

Adverse events will be monitored by the Clinical PIs (Drs. [name], [name], [name], [name] and [name]) in real-time. In addition, AEs will be reviewed quarterly in the regularly scheduled quality assurance meetings of UCSF Airway Clinical Research Center, which is attended by Drs. [name], [name], [name], and [name] and a UCSF patient safety representative.

## **14 STATISTICAL METHODS AND CONSIDERATIONS**

Prior to the analysis of the final study data, a detailed Statistical Analysis Plan (SAP) will be written describing all analyses that will be performed. The SAP will contain any modifications to the analysis plan described below.

